Spontaneous Bacterial Peritonitis	
All ascitic subjects will get paracentesis prior to Randomization (if not previously obtained within 7 days of Randomization)
	
If SBP is suspected, paracentesis is to be performed. Follow the algorithm:
 
 • IV ceftriaxone × 7 days or norfloxacin BID for 7 days (or equivalent) in subjects who have GI bleeding. • Subjects surviving an episode prior to the study or had SBP while in the study will start long-term prophylaxis with daily norfloxacin (or trimethoprim-sulfamethoxazole or equivalent); if indicated, long-term antibiotic prophylaxis can be started at Randomization or following an episode of SBP occurring bet. Study Day 1- 91. • Subjects with cirrhosis and ascites but no GI bleed are to start on long-term prophylaxis with 		

Standards of Care (SOC) for Treated and Control Subjects	Screening	Randomization (Study Start) through Hospitalization	Post Hospital Discharge	Comments
		
daily norfloxacin (or trimethoprim-sulfamethoxazole or equivalent) if ascitic fluid protein is < 1.5g/dL and at least 1 of the following is present: serum creatinine ≥ 1.2 mg/dL, blood urea nitrogen ≥ 25 mg/dL, serum sodium ≤ 130 mEq/L, and Child-Pugh ≥ 9 points with bilirubin ≥ 3 mg/dL.
		
Thrombocytopenia		
For a platelet count < 20,000/mm³ without clinical manifestations of bleeding during study treatment (ELAD and Control) will receive platelet transfusions based on the judgment of the clinical team. If the platelet count is < 20,000/mm³ and clinical manifestations of only localized contained bleeding, (ELAD and Control) subjects are to receive platelets. Subjects with platelet count of < 20,000/mm³ and generalized bleeding are to be promptly assessed, and if on ELAD, considered for treatment discontinuation.
		
Nutritional Support		
Dietary consultations within 72 hours of Randomization. If not available, the Investigator must provide dietary/nutritional supervision. Continuous Dietary follow-up throughout and at discharge.
	
Dietary to see at each follow-up visit
	

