In general, laboratory changes in these critically-ill subjects should not be recorded as AEs. However in certain cases abnormal laboratory changes should be reported as AEs. The suggested laboratory values for hematology, serum chemistry, and urinalysis parameters that occur while the subject is on ELAD treatment that should be reported as AEs are listed in the Investigator's Brochure.

If the subject develops a laboratory abnormality meeting these criteria, a clinical diagnosis should be provided with the reported laboratory abnormality, if applicable. For example, if the subject developed hematuria in the presence of >1.0 g/dL of hemoglobin, hematuria should be listed as the clinical event and include in the details of the AE that a decrease in hemoglobin was associated with the hematuria.

If the laboratory abnormality was not associated with a clinical event, the laboratory abnormality should be listed as an AE and indicate that no clinical findings were present. For example, hyponatremia is not usually associated with any specific clinical diagnosis but is found in

subjects with clinically significant decompensated liver disease, so the specific diagnosis would not be included.

The specific notable laboratory changes for hematology, serum chemistry, and the urinalysis while on ELAD to be reported as AEs are as follows:

Hematology

- Hemoglobin >1.0 g/dL decrease from Baseline in the absence of gastrointestinal bleeding or other clinically overt sources of bleeding (e.g., hematuria, central line bleeding) or hemoglobin levels <7.0 g/dL
- WBC counts <1.5 × 10³/mL in the absence of sepsis or an uncontrolled infection
- Platelet counts <20,000 × 10³/mL and note if there is evidence of impaired clotting or clinical bleeding or oozing

Serum Chemistry

- Abrupt (within 48 hours) reduction in kidney function defined as an absolute increase in serum creatinine of 0.3 mg/dL [≥ 26.4 $\mu\text{mol/L}$ or increase of serum creatinine of 50% or more (1.5-fold) from baseline]
- Hyperglycemia (serum glucose >350 mg/dL)
- Hyperkalemia (serum potassium >7.0 mEq/L)
- Hypocalcemia (serum calcium <3.5 mmol/L)
- Hypoglycemia (serum glucose <50 mg/dL)
- Hypokalemia (serum potassium <2.0 mEq/L)
- Hypomagnesemia (serum magnesium <1.0 mEq/L)
- Hyponatremia (serum sodium <120 mEq/L)
- Hypophosphatemia (serum phosphate <0.3 mmol/L)
- Lactate >4 mmol/L

Urinalysis

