Systemic inflammatory response syndrome (SIRS) is defined as two or more of the following variables being present concurrently:

- Fever of more than 38°C (100.4°F) or less than 36°C (96.8°F);
- Heart rate of more than 90 beats per minute;
- Respiratory rate of more than 20 breaths per minute;
- Abnormal white blood cell count (>12,000/µL or <4,000/µL).

The numbers of subjects with SIRS at baseline will be summarized for each treatment group.

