8.5 CHEMISTRY, HEMATOLOGY, COAGULATION, DISEASE-SPECIFIC EVALUATIONS

Data will be summarized by treatment group based on means by study visit, and mean (both absolute and %) changes from baseline by study visit. The baseline evaluation of a laboratory parameter is defined as the last evaluation of that parameter prior to randomization date/time. Additional summaries of changes relative to ELAD start date/time will be provided for subjects in the ELAD treatment group. For comparison purpose, changes relative to End of Study Day 2 will be summarized for the Control treatment group. Laboratory data will be prioritized over MELD/Maddrey data, if more than one measurement is recorded on the same study day.

For the following lab tests, proportion of subjects meeting the specified criteria will be presented by treatment group at each study visit:

- Bilirubin: <12 mg/dL vs. ≥12 mg/dL;
- Bilirubin: <16 mg/dL vs. ≥16 mg/dL;
- Hemoglobin: <7 g/dL;
- Platelet count: ≤20,000/mL;
- INR: >2.5 and >3.5;
- Calcium: ≤0.88 mmol/L;
- Glucose: >350 mg/dL or <50 mg/dL;
- Lactate: >4 mmol/L;
- Magnesium: <1.0 mEq/L;
- Phosphorus: <0.3 mmol/L;
- Potassium: >7.0 mEq/L or <2.0 mEq/L;
- Creatinine: Change <0.3 mg/dL vs. Change ≥0.3 mg/dL;
- Sodium: <130 mEq/L vs. ≥130 mEq/L;
- Sodium: <120 mEq/L.

No inferential statistical analyses will be performed for the summaries of laboratory data.

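### Three laboratory thresholds carry wrong units: calcium and WBC in Protocol Appendix D, and the platelet cut-off in SAP 8.5

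*Protocol*

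**What the plan says.** **Calcium.** Protocol Appendix D (Clinically-Significant Laboratory Changes While on ELAD Treatment, Serum Chemistry) gives "Hypocalcemia (serum calcium <3.5 mmol/L" as a change to be reported as an AE. Protocol 5.1.3, which gives examples of severe metabolic abnormality at pre-screening, puts hypocalcemia at or below 3.52 mg/dL, 0.88 mmol/L or 1.76 mEq/L. SAP 8.5 tabulates "Calcium: ≤0.88 mmol/L".

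**White cells.** The Hematology part of the same Appendix D list has "WBC counts <1.5 × 10³/mL in the absence of sepsis". The SIRS definition in SAP 4.4.4.2 uses a different scale: "Abnormal white blood cell count (>12,000/µL or <4,000/µL".

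**Platelets.** SAP 8.5 tabulates "Platelet count: ≤20,000/mL". Protocol 5.4.1.9 and Table 4 work per mm³; Table 4 reads "For a platelet count < 20,000/mm³ without clinical manifestations of bleeding". Appendix D's own platelet line is below 20,000 × 10³/mL.

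**The concern.** These figures are operative. The Appendix D values tell sites what to report as an AE while a subject is on ELAD, and the SAP 8.5 values define rows of a by-visit safety table. AE incidences are then compared between groups (Protocol 7.6, SAP 8.3).

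The calcium line matters most because its error runs in one direction and touches one arm. A trigger set too high adds AEs, and the list applies only on ELAD, so any excess would appear as a between-group difference in hypocalcemia. Appendix D already lists hypocalcemia as an expected event for the ELAD System, so an excess produced by the unit could pass as a real effect.

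The other two errors run the opposite way. A WBC trigger set far too low prompts nothing, and a platelet cut-off set far too low yields an empty row that a reader could take as evidence of no severe thrombocytopenia.

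**Working it through.** **Inputs.** Calcium: <3.5 mmol/L (Protocol Appendix D); 3.52 mg/dL = 0.88 mmol/L = 1.76 mEq/L (Protocol 5.1.3); ≤0.88 mmol/L (SAP 8.5). WBC: <1.5 × 10³/mL (Appendix D); 4,000 and 12,000/µL (SAP 4.4.4.2). Platelets: ≤20,000/mL (SAP 8.5); <20,000 × 10³/mL (Appendix D); <20,000/mm³ (Protocol 5.4.1.9 and Table 4).

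**Formulas.** Calcium: mmol/L = mg/dL × 10 / 40.08, and mEq/L = 2 × mmol/L. Counts: 1 mL = 1,000 µL = 1,000 mm³.

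**Step 1. Reproduce the protocol's own conversion.** 3.52 × 10 / 40.08 = 0.878 mmol/L, and 2 × 0.878 = 1.757 mEq/L. Both agree with 5.1.3, so its three calcium figures are consistent with each other.

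**Step 2. Appendix D calcium.** The ratio in 5.1.3 is 3.52 / 0.88 = 4.0 mg/dL per mmol/L.
- As printed: 3.5 mmol/L × 4.0 = 14.0 mg/dL, and 3.5 / 0.88 = 3.98 times the limit in 5.1.3 and SAP 8.5.
- If 3.5 was meant as mg/dL: 3.5 × 10 / 40.08 = 0.873 mmol/L, which agrees with 0.88.
- If 3.5 was meant as mEq/L: 3.5 / 2 = 1.75 mmol/L, which does not agree.

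The neighbouring lines support a label error. The Appendix D cut-offs for glucose, potassium, magnesium, sodium, phosphate, lactate and creatinine change use the same numbers and units as SAP 8.5. Among the chemistry lines, only calcium differs.

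**Step 3. Appendix D WBC.** 1.5 × 10³ / 1,000 = 1.5 cells/µL. The SAP's low-WBC limit is 4,000/µL, and 4,000 / 1.5 ≈ 2,667. Read per µL, the line becomes 1,500/µL, on the scale used in the SAP.

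**Step 4. Platelets.**
- SAP 8.5: 20,000 / 1,000 = 20/mm³, and 20,000 / 20 = 1,000-fold below the protocol's level.
- Appendix D: 20,000 × 10³ / 1,000 = 20,000/mm³, equal to the protocol's level.

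**Step 5. Could a lost micro sign explain the counts?** The micro sign is legible in Appendix D (the creatinine line, µmol/L) and in the SAP (SIRS, per µL). The WBC and platelet lines in Appendix D also share the unit × 10³/mL. If mL is right, WBC is 1,000-fold too low. If µL was meant in both, platelets become 20 million/µL. No single unit makes both lines right. The calcium line involves no micro sign.

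**The case against.** The best case against is that these are typographical slips with limited reach. Much of it stands.

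- **Severe thrombocytopenia and leukopenia going unflagged.** A reader might infer this, but the documents do not support it. Appendix D's platelet line is correct and still prompts an AE below 20,000/mm³ on ELAD. Protocol 9.3 makes an isolated laboratory abnormality an AE if it limits treatment, leads to intervention or concerns the investigator, whatever Appendix D says. SAP 8.5 also gives means and changes by visit, and SAP 8.3 tabulates AEs by preferred term.
- **Two empty table rows.** SAP 8.5 has no WBC threshold row. The WBC figure is only an AE prompt, so one row is affected.
- **A wrong calcium table.** SAP 8.5's calcium row is right, and it is built from laboratory values in both groups. Only AE reporting by sites is exposed.
- **Sites would not apply 3.5 mmol/L literally.** The line is headed hypocalcemia, the section says that laboratory changes should in general not be AEs, it calls the values suggested, and it refers to the Investigator's Brochure, which was not available for this review. This makes mass over-reporting a literal worst case. It does not remove the conflict, because Appendix D goes on to print the list as changes to be reported.
- **The SAP takes precedence.** SAP 1.1 lets the SAP override the protocol where analysis instructions conflict, other than for obvious typographical errors. A site's AE-reporting rule is not an analysis instruction, so the clause does not cure calcium or WBC. For platelets, the exception leaves the programmer to decide whether the unit is an obvious error.

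**Conclusion.** All three unit errors stand. Appendix D calcium is about four times the limit used elsewhere (14.0 against 3.52 mg/dL). Appendix D WBC works out at 1.5 cells/µL, so the trigger would in practice never be met. The SAP 8.5 platelet cut-off is 1,000-fold too low, so its row would be empty if programmed as written.

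Two assumptions carry the practical consequences, since the documents give no reference ranges. First, serum calcium on ELAD is nearly always below 14.0 mg/dL; that is why the literal rule would reach almost every ELAD subject. Second, counts of 1.5 WBC/µL or 20 platelets/mm³ are possible in principle but not expected. How far sites actually followed the calcium line cannot be judged from the documents.

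The effect is limited to AE capture and one descriptive row. SAP 8.5 plans no inferential analysis of laboratory data, and the log-rank test, its alpha, the power and the sample size are untouched. No eligibility or transfusion limit is in question; the point concerns reporting and tabulation units only.

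**What to change.** 1. Protocol Appendix D, calcium: reconcile the unit with Protocol 5.1.3 and SAP 8.5.
2. Protocol Appendix D, WBC: express the threshold per µL.
3. SAP 8.5, platelets: express the cut-off per mm³, as in Protocol 5.4.1.9 and Table 4.
4. Leave Appendix D's platelet line and SAP 8.5's calcium row as they are.
5. Check the matching list in the Investigator's Brochure for the same three lines.
6. Review hypocalcemia AEs already reported for ELAD subjects against the recorded calcium values, to see whether any rest on the literal rule.

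Items 1 to 3 are administrative corrections and need no new data; the platelet row can be rebuilt from counts already collected. Item 6 is a limited data review, needed only if sites worked from the printed calcium value.

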Appendix E. Anticoagulation Guidelines for the VTL-308 Study

Anticoagulation Guidelines During ELAD Treatment

In general, standard anticoagulation protocols of the Investigational institution for the administration of extracorporeal procedures should be applied during the administration of ELAD treatment. However, there may be a requirement for more rigorous monitoring.

As a general guideline, subjects who are administered ELAD that have a baseline PTT of <50 seconds or an activated clotting time (ACT) of <150 seconds may require heparin in order to prevent rapid clotting in the ELAD extracorporeal blood circuit. In such cases, the initial dose applied may be as small as 200-400 Units of non-fractionated heparin per hour into the arterial line of the blood circuit, and a control sample should be taken within 1 hour of initiation of heparin treatment in order to assess the impact of the heparin dosing on coagulation status. If the PTT is >80 seconds, or the ACT is >200 seconds, the dose should be reduced, e.g. by half and a control sample should be taken within 1 hour of the adjustment of the heparin dose. If the PTT is still <50 seconds and the ACT is still <150 seconds, the dose should be increased, e.g. doubled and a control sample should be taken within 1 hour of the adjustment of the heparin dose.

The goal is to maintain PTT between 50 and 80 seconds or the ACT between 150 and 200 seconds in the case of non-fractionated heparin use.

For alternative anticoagulants, such as hirudin, or fractionated heparin, institutional protocols for CVVH therapy may be applied, but must be monitored rigorously.

CITRATE MUST NOT BE USED as an anticoagulant during ELAD treatment.

A formal heparin-based protocol for extracorporeal therapy of liver patients can be found in an article by Hillebrand et al¹.

1. Hillebrand, et al. Formal heparin anticoagulation protocol improves safety of charcoal-based liver assist devices. *ASAIO J.* 2006 May-Jun;52(3):334-42.

1 STUDY OBJECTIVES AND SAMPLE SIZE RATIONALE

1.1 INTRODUCTION

The purpose of the VTL-308 Statistical Analysis Plan (SAP) is to provide detailed instruction and guidance for the analysis of the VTL-308 study results. This plan is intended to be inclusive of all planned analyses and to provide the guidelines for additional analyses, should they be necessary, to interpret the pre-specified analyses or to provide further context for the interpretation of the study outcomes.

The plans outlined in the statistical section of the VTL-308 Clinical Protocol are intended to align with this SAP. However, the SAP may be subject to change based on advances in analytical standards and the availability of new information from the literature. In the event that an analysis conflict is observed between the instructions in the protocol and this SAP (other than obvious administrative or typographical errors), the SAP shall supersede the protocol.

There are a number of types of ACLF, including acute flare of chronic hepatitis B and alcohol-induced liver decompensation (AILD). AILD is defined as a progressive inflammatory liver disease leading to an acute form of alcohol-induced liver injury which arises when the proximate cause of the acute decompensation is the consumption of alcohol. A specific, well-defined subset of AILD is severe alcoholic hepatitis (sAH), generally defined as progressive inflammatory liver disease leading to an acute form of alcohol-induced liver injury that occurs with the consumption of large amounts of alcohol in patients with relatively mild, underlying chronic alcoholic liver disease ([Dubuquoy et al. 2015](#), [Shi et al. 2015](#)). Based on current literature and analysis of the VTI-208 ELAD clinical data, it is evident that the diagnosis of all subjects enrolled in VTI-208 fit into the category of sAH. As sAH is the more commonly used clinical term, from this point forward, sAH will be used to refer to the indication, rather than AILD.

1.2 ANALYSIS OBJECTIVES

1.2.1 Primary Objective

The primary objective of the study is to evaluate safety and efficacy of ELAD with respect to overall survival (OS) of subjects with a clinical diagnosis of sAH through at least Study Day 91, with follow-up Protocol VTL-308E providing additional survival data up to a maximum of 5 years, that will be included, as available, through VTL-308 study completion (after the last surviving enrolled subject completes Study Day 91 visit; incorporation of data from VTL-308E is further described in [Section 2](#) and [Section 7.1.1](#)). The primary objective will be assessed using a log-rank analysis of survival data conducted in the Intent-to-Treat (ITT) population.

1.2.2 Secondary Objectives

The secondary objectives are defined as:

- To estimate the effect of ELAD on the proportion of survivors at Study Day 28 and Study Day 91 using a Chi-squared test;
- To estimate the effect of ELAD on the proportion of subjects achieving a 20% reduction in total bilirubin by Day 7 (ECBL20 Yes);

1.2.3 Exploratory Objectives

The exploratory objectives will identify potential differences between treatment groups in factors related to liver transplant, standard demographics, selected baseline characteristics, medical history, and standard of care. These factors are pre-specified in this SAP, and are based on previously identified and medically pertinent influences on treatment outcomes in alcoholic hepatitis, as well as on factors shown to be important in prior studies of ELAD. In addition, the relationship between outcomes and ELAD System performance, therapeutic interventions of interest, and administration of concomitant pharmacotherapies of interest will be assessed in order to help inform product labeling and use. Analyses of post-treatment medical care and behavior will also be carried out to assess whether there are differences between ELAD-treated and Control subjects and whether those differences have an impact on treatment outcomes. Furthermore, the difference between treatment groups at each time point of selected labs and MELD scores with a mixed model repeated measure (MMRM) will be analyzed. Changes in certain biomarkers of interest will also be evaluated (See [Section 7.3](#)).

1.2.4 Safety Assessments

Safety Assessments are discussed in [Section 8](#) and will include analyses of adverse events, changes in medical conditions, changes in vital signs, and changes in clinical laboratory values.

1.3 SAMPLE SIZE RATIONALE

The sample size is based on experience from the VTI-208 study.

The VTL-308 inclusion criteria have been established to reflect a subset of the VTI-208 population, i.e. the VTI-208 population with baseline criteria of MELD <30, age <50, INR \leq 2.5, creatinine <1.3 mg/dL and serum total bilirubin \geq 16 mg/dL.

The key design feature of the VTL-308 Protocol is that the primary analysis of treatment effect on overall survival is based on a log-rank statistic having two-sided significance level of 0.05. This primary analysis will be performed when the last of 150 randomized subjects has been followed for at least 91 days. Sample size adjustments may be made only in the instance in which more than 150 randomized subjects would be needed in order to achieve the minimum threshold of 55 deaths at the time of that analysis.

When the study is nearing completion of enrollment, the total number of deaths occurring through that time will be calculated, along with the mortality rate, based on the enrollment rate per month and the time to death. Based on these calculations a projection will be made of the total number of subjects that will need to be enrolled to achieve the minimum threshold of 55 deaths at the time of study data lock (estimated to be approximately 5 months after last patient enrolled). The total sample size may then be adjusted accordingly.

Analysis of the VTI-208 data suggests that in a group of subjects meeting the inclusion criteria for VTL-308, it might be reasonably anticipated that one-year survival will be in the range from 40% to 48% in the Control group. Under the assumption of a proportional hazards model, if the hazard ratio is 0.4 in favor of the ELAD group, this leads to the anticipation that one-year survival will be in the range from 69.5% to 74.5% in the ELAD subjects.

The rationale for the sample size is based on the following assumptions:

- the analysis of the primary endpoint of overall survival will be conducted in the ITT population;
- the prospectively defined population behaves similarly to the corresponding subgroup of the VTI-208 study;
- the log-rank test will be used to compare two survival curves using a two-sided significance level of 0.05;
- one-year survival will be in the range from 40% to 48% in the Control group and in the range from 69.5% to 74.5% in the ELAD group;
- the accrual distribution will be uniform with an accrual time that will be at least 720 days;
- the rate of missing data will be in the range from 0% to 10%; and
- the primary analysis will be the time when at least 55 deaths have occurred and the time when the last enrolled subject has been followed for at least 91 days. It follows that a sample size for the VTL-308 trial of 75 subjects per group with 1:1 allocation would provide a number of events (i.e., deaths) in the range from 55 to 65, even if we assume average follow-up of only 1 year. With 55 events, the trial will have 90% power if the true hazard ratio is 0.417; with 65 events, the trial will have 90% power if the true hazard ratio is 0.447.

2 STUDY DESIGN

VTL-308 is a randomized, open-label, multicenter, controlled, pivotal study of subjects with sAH. A minimum of 150 subjects meeting the eligibility requirements of the study will be randomly assigned in a 1:1 ratio at site level to receive either standard of care treatment for sAH (as defined in the protocol) plus treatment with the ELAD System (ELAD group) or standard of care treatment for sAH (as defined in the protocol) alone (Control group).

Central randomization will be performed to ensure that neither site nor study personnel will have any foreknowledge of subject treatment assignment.

Because ELAD treatment must take place in an Intensive Care Unit (ICU), or a Step-Down Unit (SDU) with an equivalent standard of care if written pre-approval has been given by VTL, all subjects considered for enrollment must be considered eligible for ICU or SDU placement. Control subjects need not be placed in an ICU or SDU setting unless deemed necessary by the investigator due to the severity of their illness.

Screening evaluations and assessments will be completed for both ELAD and Control subjects and reviewed against inclusion/exclusion criteria prior to Randomization. For both study groups, ELAD-treated and Control, the time of Randomization will define the time of study entry (Hour 0, Study Day 1, study baseline) and inclusion in the ITT population. Laboratory draws for the first post-randomization blood tests required by the protocol will begin with the next standard laboratory draw (typically the following morning).

In addition to the Screening evaluations, because there will be a delay between Randomization and initiation of ELAD treatment, a further assessment to confirm the subject's safety eligibility will be undertaken. This assessment will be conducted in the same manner for both ELAD and Control subjects. Either the principal investigator or sub-investigator trained on the study must have evaluated the safety eligibility results and be immediately available when ELAD treatment begins in order to assess changes in the subject's condition since Randomization. This is especially important when evaluating changes during the 24 hours preceding initiation of ELAD treatment in order to determine whether the subject remains eligible for extracorporeal treatment.

For all subjects randomized, the following key safety factors must be evaluated within 6 hours prior to ELAD treatment initiation, or at End of Study Day 2 (\pm 6 hours) for Control subjects. These include:

- Platelet count;
- International normalized ratio (INR);
- Serum creatinine;
- Evidence of infection unresponsive to antibiotics;
- Hemodynamic instability assessment (blood pressure and MAP);
- Bleeding status;
- Status with respect to ventilation, intubation, or need for hemodialysis.

These factors will be assessed in accord with the pertinent exclusion criteria (2, 3, 4, 7, 9, 10, 15, and 16, relative to the safety evaluation time point) in the VTL-308 Study Protocol (Amendment

1, dated 20 November 2015). Subjects must be assessed within 6 hours prior to ELAD treatment initiation, or at End of Study Day 2 (± 6 hours) for Control subjects, and subjects must continue to be eligible based on these exclusion criteria, at this time point, to remain in the modified intent-to-treat (mITT) population.

In addition, vital signs will be taken, total bilirubin measured and a MELD score will be calculated at this time point.

The standard of care labs may fulfill this requirement provided they are drawn within 6 hours prior to ELAD treatment initiation.

- If an ELAD subject fails to meet these criteria, ELAD treatment will not be initiated, the subject will continue to receive standard of care, and the subject will be excluded from the mITT population;
- If a Control subject fails to meet these criteria, the subject will continue to receive standard of care, and the subject will be excluded from the mITT population.

Subjects randomized to the ELAD group will be treated with ELAD for a minimum of 3 days (72 hours).

ELAD treatment may be interrupted for a period of *less* than 6 hours then restarted with the same set of cartridges provided that, in the opinion of the investigator, the subject remains eligible for treatment. ELAD treatment may be interrupted for a period of *more* than 6 hours but *less* than 72 hours, for example, to allow for the conduct of a diagnostic or therapeutic procedure or for management of an adverse event, or should there be a need to interrupt the use of anticoagulants. Should this circumstance arise, a new set of ELAD cartridges must be used if treatment of the subject will continue, and the subject must meet the same safety eligibility criteria as are required prior to the initiation of treatment.

ELAD treatment will be discontinued and will not be restarted if any of the following discontinuation criteria are met. If ELAD treatment is discontinued, subjects will receive standard of care therapy alone and be followed through Study Day 91. Discontinuation criteria include the following:

- Continued ELAD treatment is judged to be futile, defined as an increase of more than 25% in total bilirubin at 72 (+6) hours (includes clinical consideration of impact of artifactual hyperbilirubinemia) compared to the most temporal measurement of total bilirubin taken within 6 hours prior to ELAD initiation. Bilirubin measurements must be taken at least 12 hours after any procedure known to artificially alter serum bilirubin (e.g., administration of packed red blood cells, plasma exchange);
- Subject has been off treatment for more than 72 hours;
- Subject has suffered an adverse event that, in the investigator's opinion, requires ELAD treatment to be discontinued, and which cannot be resolved within a period of 72 hours;
- Subject has suffered a disseminated intravascular coagulopathy (DIC) event;
- Subject develops an indication for hemodialysis;

- Subject requires an extracorporeal procedure that takes precedence over ELAD treatment;
- Subject has been treated for a maximum of 120 hours within five (5) 24-hour periods regardless of treatment interruption;
- Subject undergoes orthotopic liver transplantation;
- Subject is discharged from the hospital;
- The first set of ELAD cartridges has been replaced for any reason and the second set also requires replacement, or the subject fails safety eligibility checks for the second set;
- Subject or legally authorized representative withdraws consent for further ELAD treatment;
- Investigator decides to stop ELAD treatment;
- ELAD System performance issues arise that cannot be resolved within a period of 72 hours;
- Subject experiences catheter-related issues that cannot be resolved within a period of 72 hours.

Subjects in both groups will be evaluated throughout the 91-day study period.

Subjects undergoing orthotopic liver transplantation during ELAD treatment will be evaluated exactly the same as any other subject who completed treatment early. The evaluation mandated for the first day after treatment will be carried out 24 hours post-transplantation. All subjects (ELAD and Control) receiving a liver transplant will be followed through Study Day 91 and also in Study VTL-308E in an identical manner to subjects who did not receive a liver transplant.

If standard of care treatment as defined by the institution is consistent with discharging the subject home, then the subject should be discharged. Prior to discharge, the subject will be advised to attend all protocol-required visits. Instructions for home visits will also be reviewed.

An extension of this study, VTL-308E, will provide extended follow-up of subjects enrolled in VTL-308 over a period of 5 years to determine survival, incidence of cancer, liver transplant, and quality of life. Data obtained from the extension study will provide additional survival data up to a maximum of 5 years that will be included, as available, through VTL-308 study termination (after the last surviving enrolled subject completes Study Day 91).

